### **6.3.9 Safety Follow-up**

A 2-week safety follow-up telephone contact is to be completed for all subjects. Subjects will have the following completed via telephone approximately 2 weeks after the last dose of study drug:

- Assessment of concomitant medications/treatments
- Assessment of AEs

Subjects who discontinue early or complete the study should return to standard of care. The Sponsor will provide investigative sites with 3 months of after-study assistance to transition subjects to standard of care therapy after their participation in the study.

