5.2.1 Hamilton Depression Rating Scale 17-Items (HAMD-17)

The HAMD-17 is assessed at Screening, Baseline, Weeks 2, 4, 6, and Week 8/ET visits.

The HAMD-17 is a 17-item clinician-administered questionnaire used to provide an indication of depression, and as a guide to evaluate recovery (Hamilton, 1960). The

questionnaire assesses symptoms over the past week (7 days). The questionnaire is designed for adults to rate the severity of, and change in, depressive symptoms by probing mood, feelings of guilt, suicide ideation, insomnia, agitation or retardation, anxiety, weight loss, and somatic symptoms. Each item on the questionnaire is scored on a 3- or 5-point scale, depending on the item, and the total score is compared to the corresponding descriptor. The HAMD-17 total score can range from a minimum of 0 to a maximum of 52. A score of 0-7 is considered normal. Scores of 14 or higher indicate moderate, severe, or very severe depression.

If more than 3 items are missing, the total score will be set to missing. If 3 or fewer items are missing, then missing items will be imputed as follows:

- Items using a 3-point scale (4, 5, 6, 12, 13, 14, 16, and 17): missing values will be imputed using the arithmetic mean of the non-missing items that are also scored on a 3-point scale, then rounded to the nearest integer
- Items using a 5-point scale (1, 2, 3, 7, 8, 9, 10, 11, and 15): missing values will be imputed using the arithmetic mean of the non-missing items that are also scored on a 5-point scale, then rounded to the nearest integer

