5.3 Analysis Visit Windows

Baseline will be defined as the last non-missing result, including results from repeated and unscheduled measurements, before dosing.

Efficacy and safety assessments will be summarized by analysis visit as shown in [Table 2](#) below.

Table 2 Analysis Visit Windows

Analysis Visit Name	Study Visit	Target Study Day ¹	Study Day Interval
Baseline	Visit 2 (Baseline)	1	≤ 1
Week 2	Visit 3 (Week 2)	15	2 to 21
Week 4	Visit 4 (Week 4)	29	22 to 35
Week 6	Visit 5 (Week 6)	43	36 to 49
Week 8	Visit 6 (Week 8/ET)	57	50 to 63
Follow-up	Visit 7 (Week 10/Safety Follow-up)	71	≥ 64

¹ Study day = assessment date - first dose date + 1 if the assessment date \geq first dose date, otherwise study day = assessment date - first dose date. Study day 1 is the day of first administration of study drug (pimavanserin).

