5.3.1 Unscheduled Assessments

Both scheduled and unscheduled assessments, including the assessments at ET visits, will be considered for planned timepoint analyses. All assessments will be presented in data listings.

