13.1.1 Primary Analysis using MMRM in the Full Analysis Set

The HAMD-17 total score will be analyzed using mixed model repeated measures (MMRM) in the Full Analysis Set. The dependent variable will be the change from Baseline in the

HAMD-17 total score. The independent variables in the model will include the following: visit (Week 2, Week 4, Week 6, and Week 8), Baseline-by-visit interaction, and the Baseline HAMD-17 total score as a continuous covariate. An unstructured covariance matrix will be used and the Kenward-Roger approximation will be used to adjust the denominator degrees of freedom. Least squares (LS) adjusted means will be estimated using observed cases (OC).

In the event that the model fails to converge using the unstructured covariance matrix, then the following covariance structures will be modeled in the order given: heterogeneous Toeplitz, heterogeneous compound symmetry, heterogeneous autoregressive(1), Toeplitz, compound symmetry, autoregressive(1), variance components. The first covariance structure that allows for convergence will be selected for the final model.

Summary statistics for the HAMD-17 total score (observed and change from Baseline) will be presented for all visits from Baseline through Week 8. For change from Baseline values at each post-Baseline visit, LS means and standard errors (SE), the corresponding 95% confidence interval and p-value will also be presented. In addition, LS mean \pm SE over time for the change from Baseline values will also be presented in line plots.

The hypothesis testing will be performed based on the LS mean change at Week 8 and will be tested at an alpha level of 0.05 (2-sided).

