13.1.5 HAMD-17 Responder Analysis

For the HAMD-17 total score, a treatment response is defined as a $\geq 50\%$ reduction from Baseline.

At each timepoint the proportion of responders will be descriptively summarized including 95% confidence intervals. Both OC, in which subjects with missing values at a given visit are excluded, as well as missing values imputed as non-responders will be presented.

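### SAP Table 2 gives a Week 8 clinic visit held on Day 64 or later to the telephone Follow-up, so a completed HAMD-17 can go unused at Week 8; the effect is small and the repair is one table row

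*SAP*

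**What the plan says.** SAP 5.3 sets the assignment rule: "Efficacy and safety assessments will be summarized by analysis visit as shown in" Table 2. There, Week 8 has target Day 57 and interval Day 50 to 63. Follow-up has target Day 71 and covers Day 64 onward with no upper limit; its study visit is "Visit 7 (Week 10/Safety Follow-up".

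The schedule of assessments (Protocol Table S-1, SAP Table 1) places the Week 8 visit on Days 54 to 60. Visit 7 is a call. Protocol 6.3.9 states "Subjects will have the following completed via telephone approximately 2 weeks after the last dose of study drug", and then lists only concomitant medications or treatments and adverse events. SAP 5.2.1 confirms that no depression rating is planned there: "The HAMD-17 is assessed at Screening, Baseline, Weeks 2, 4, 6, and Week 8/ET visits".

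SAP 5.3.1 adds that "Both scheduled and unscheduled assessments, including the assessments at ET visits, will be considered for planned timepoint analyses". It makes no exception for a Week 8 visit after Day 63. SAP 5.3.2 covers the choice among several values inside one window and refers details to a separate programming document, which is not part of the plan reviewed here.

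For the primary analysis (SAP 13.1.1), "The hypothesis testing will be performed based on the LS mean change at Week 8 and will be tested at an alpha level of 0.05", using observed cases at Weeks 2, 4, 6 and 8. SAP 13.1.5 reports responders on observed cases, and "as well as missing values imputed as non-responders will be presented". SAP 13.1.7 does the same for dichotomised CGI-I.

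**The concern.** A boundary halfway between two visits makes sense when both visits measure the same thing. Here the later visit measures no scale, so an efficacy rating assigned to Follow-up has no analysis to enter. A subject who finishes treatment and completes a HAMD-17 a few days late would be treated at Week 8 as if no rating had been made.

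At stake is the tested time point of the primary endpoint, in an open-label study planned around 34 evaluable subjects. SCOPA, EQ-5D-5L, MMSE and UPDRS Part III have only two post-Baseline visits, Weeks 4 and 8. Laboratory tests and physical and neurological examinations have only Week 8. If the handling of late visits is not written down, it would have to be settled by people who already know the subjects' results.

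**Working it through.** **1. Day arithmetic** (SAP Table 2 and the schedule of assessments)

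- Days past the end of the scheduled Week 8 window: 64 - 60 = 4.
- Days past the Week 8 target: 64 - 57 = 7.
- Midpoint of the Week 8 and Follow-up targets: (57 + 71)/2 = 64.
- Table 2 thus accepts a Week 8 rating 7 days early (Day 50) but only 6 days late (Day 63).

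**2. One subject traced through the plan.** Take a complete HAMD-17 on Day 64 and no other rating in Days 50-63.

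| Analysis | What happens |
|---|---|
| Full Analysis Set (SAP 4.2) | Subject stays in |
| Primary MMRM (SAP 13.1.1) | Weeks 2-6 contribute; the observed Week 8 score does not |
| LOCF paired t-test (SAP 13.1.2) | Earlier value used at Week 8, normally Week 6 |
| Responders and CGI-I, observed cases (SAP 13.1.5, 13.1.7) | Excluded at Week 8 |
| Responders and CGI-I, missing imputed | Counted as non-responder or not improved |
| SCOPA, EQ-5D-5L, MMSE, UPDRS Part III | Week 8 value lost, Week 4 kept |
| Laboratory and examination tables by visit | The only scheduled post-Baseline value is lost |
| Overall minimum, maximum and potentially clinically important tables | Value kept (SAP 5.3.2) |

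**3. The plan's own sample size** (SAP 3.5: SD 6.0, mean change 3, two-sided 0.05, paired t-test)

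Power comes from the noncentral t distribution with n - 1 degrees of freedom and noncentrality (3/6.0) × √n. At n = 34 the noncentrality is 0.5 × 5.831 = 2.915 and power is 80.8%. This is the smallest n that reaches 80%. Allowing for 15% non-evaluable, 34/0.85 = 40. The plan's 34 and 40 are both reproduced.

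**4. Effect of lost Week 8 values on power.** The documents give no count of late visits, so one to three is an assumption.

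| Week 8 values lost | Starting from 34 | Starting from 40 |
|---|---|---|
| 0 | 80.8% | 86.9% |
| 1 | 79.5% | 86.1% |
| 2 | 78.2% | 85.1% |
| 3 | 76.8% | 84.1% |

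The first column supposes that the other six enrolled subjects are already non-evaluable. Both columns overstate the loss for the primary analysis, because the MMRM also draws on Weeks 2-6.

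**5. Effect on the imputed response rate.** Each true responder counted as a failure costs 1/40 = 2.5 points to 1/34 = 2.9 points. A late subject who is not a responder changes nothing. Three late visits cost at most 3/40 = 7.5 to 3/34 = 8.8 points, and only if all three are responders.

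**The case against.** The cut-off is conventional. Weeks 4, 6 and 8 all have 14-day intervals from 7 days before target to 6 days after, and the Week 8 interval is already twice the 7-day scheduled window. Leaving a rating taken a week past target out of an 8-week endpoint can be defended, perhaps to keep off-drug ratings out. This stands as a reason for some upper limit. It does not justify this one: the SAP gives no such purpose, and a calendar-day rule serves it poorly. Days 50-63 can admit a rating made after dosing stopped, while Day 64 excludes one made on drug.

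The Follow-up row is also not useless for clinic data. Protocol 6.4 allows unscheduled visits with vital signs and further safety evaluations, and a recheck after treatment belongs there. That stands, so the row should not be confined to data from the call. Nor should the Week 8 window simply end 7 days after the last dose. With a last dose on Day 54, such a limit falls on Day 61 and would remove a Day 62 rating that the SAP now keeps.

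A reader might infer that a late subject is lost to the primary analysis and simply scored a non-responder. The documents do not support that. The subject remains in the Full Analysis Set, the earlier visits remain in the MMRM, and failure is assigned only in the imputed tables. The late values are also still listed.

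**Conclusion.** The gap is real: a completed Week 8 assessment on Day 64 or later has no place in the Week 8 analyses unless another one falls in Days 50-63. The expected effect is small. It is 2.5 to 2.9 points on the imputed response rate per true responder affected, and at most 1.3 percentage points of power for a first loss when evaluable N is already 34 (80.8 - 79.5). If fewer subjects than allowed for are non-evaluable, power stays above 80%.

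These figures rest on an assumed number of late visits and on paired-t power as a bound for the MMRM. The sample size calculation is not in question. The separate programming document might cover late visits, but SAP 5.3.2 cites it for values within a window, and the SAP itself is silent. This is a cheap improvement, not a threat to the primary conclusion.

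**What to change.** Change one row of SAP Table 2 and add a footnote:

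- Keep Days 50-63 as Week 8 for every subject.
- For clinic assessments, extend the upper limit of Week 8 to the later of Day 63 and 7 days after the last dose. Seven days matches the HAMD-17 recall period in SAP 5.2.1, so the rated week still touches treatment.
- Leave the closest-to-Day-57 rule unchanged.
- Keep Follow-up for the Visit 7 call and for unscheduled safety assessments after that limit.

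Three cases show the rule. Last dose Day 63, visit Day 64: the limit is Day 70, so the rating counts. Last dose Day 54, rating Day 62: the limit stays at Day 63, so the rating is kept as now. Last dose Day 57, visit Day 66: the limit is Day 64, so the rating goes to Follow-up.

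The cost is that a few Week 8 values come from a slightly later day, and that the limit depends on the last-dose date. When that date is missing, SAP 5.4 and 12.3 substitute a drug-return or end-of-study date, which may be the late visit itself. Subjects who qualify only through a substituted date should be listed. The change should be made before database lock.

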5.3.1 Unscheduled Assessments

Both scheduled and unscheduled assessments, including the assessments at ET visits, will be considered for planned timepoint analyses. All assessments will be presented in data listings.

5.3.2 Multiple Measurements within Visit Windows

If more than one assessment falls within a given window, then the assessment closest to the target study day will be selected for the by-visit summaries. If two assessments are equidistant from the target day, then the chronologically last assessment will be used. Exceptions may be made for incomplete assessments, in which case, more complete assessments may be given priority. Details are provided in a separate programming conventions document.

For safety analysis where the most extreme values should be selected (e.g., overall post-baseline minimum, overall post-baseline maximum, and potentially clinically important values), all non-missing post-Baseline values will be considered, regardless of whether the value is selected for the by-visit summaries. All results will be presented in data listings.

When the 12-lead electrocardiogram (ECG) is collected in triplicate, the average of the triplicate parameter values will be considered as one assessment for the summaries.

5.4 Data Handling Conventions

If the last dose date of study drug is missing for a subject who completed or discontinued from the study, then the last study drug return date will be used in the calculation of treatment duration. If the study drug return dates are all missing (e.g., the subject never returned any

study drug), then the ET/EOS date (excluding follow-up visit) will be used in the calculation of treatment duration. For the incomplete last dose date of the study drug, the imputation algorithms will be detailed in the analysis dataset specification (ADS) document. The missing or incomplete dates will be displayed in the data listings as reported on the eCRF rather than the imputed dates.

For any data summarization that occurs before final database lock, if a subject is still ongoing, then that subject's last dose date will be imputed using the database extract date.

5.4.1 Missing or Incomplete Dates for Prior or Concomitant Medications

Missing or incomplete medication start or end dates will be imputed for the purpose of determining whether the medications are taken concomitantly (see [Section 10](#) for definition). When the chronological order of medication use relative to the study drug treatment period is unclear due to missing or incomplete date(s), the medication will be considered as concomitant. The imputation algorithms will be detailed in the ADS document. The missing or incomplete dates will be displayed in the data listings as reported on the eCRF rather than the imputed dates.

5.4.2 Missing or Incomplete Dates for Adverse Events

Missing or incomplete adverse event (AE) start dates will be imputed for the purpose of determining whether the AEs are treatment-emergent (see [Section 14.1](#) for definition). When the chronological order of an AE onset relative to the study drug treatment period is unclear due to missing or incomplete date(s), the AE will be considered as treatment-emergent. The imputation algorithms will be detailed in the ADS document. The missing or incomplete dates will be displayed in the data listings as reported on the eCRF rather than the imputed dates.

5.4.3 Missing Severity Assessment for Adverse Events

If the severity is missing for an AE starting on or after the date of the first dose of study drug, then a severity of “Severe” will be assigned. The imputed values for severity assessment will be used for incidence summaries, and the actual values will be used in data listings.

5.4.4 Missing Relationship to Study Drug for Adverse Events

If the relationship to study drug is missing for an AE starting on or after the date of the first dose of study drug, a causality of “Related” will be assigned. The imputed values for relationship to study drug will be used for incidence summaries, and the actual values will be presented in data listings.

5.4.5 Character Values of Clinical Laboratory Variables

If the reported value of a clinical laboratory variable cannot be used in a statistical analysis due to, for example, a character string reported for a numeric variable, an appropriately determined coded value may be used in the statistical analysis. The coding algorithms will be detailed in ADS document. The actual values as reported in the database will be presented in data listings.

6 SUBJECT DISPOSITION

For subjects who participate in the screening phase but are not enrolled in the study (i.e., screen failures), their demographics information (including age, sex, and primary race), screen failure reasons (the specific inclusion/exclusion criterion [or criteria] not met or other reason), and protocol version will be listed. If a subject is re-screened, then the re-screening subject ID and the final enrollment status (whether eventually enrolled) will also be displayed in this listing. In addition, the frequency that the screen failure reasons are reported will also be summarized. Note that one subject may be deemed ineligible for multiple inclusion/exclusion criteria and may be allowed to rescreen with the permission of the Medical Monitor, provided the screen failure was due to a temporary condition that subsequently resolved.

The number of sites that screened at least 1 subject, number of sites that enrolled at least 1 subject, number of subjects screened, and number of unique subjects screened will be summarized by site and overall. In addition, the number of subjects enrolled at each site will also be tabulated by analysis set.

For enrolled subjects, the number and percentage of subjects in Safety Analysis Set and Full Analysis Set will be summarized. A listing will be provided displaying all subjects excluded from the Safety and Full Analysis Sets, and will include reason(s) for exclusion.

Within each analysis set, the number and percentage of subjects who completed the study or discontinued (all discontinued and by discontinuation reason) will also be summarized.

7 PROTOCOL DEVIATIONS

Protocol deviations will be reviewed periodically over the course of the study. The review process, definition of the deviation categories, and the classification of a deviation as major or minor are detailed in the Protocol Deviation Management Plan.

A summary of the number and percentage of subjects with major protocol deviations for each deviation category will be presented for the Safety Analysis Set. A listing of protocol deviations by site and subject will also be provided.

8 DEMOGRAPHICS AND OTHER BASELINE CHARACTERISTICS

8.1 Demographics

Demographics will be summarized for the Safety Analysis Set and the Full Analysis Set using descriptive statistics. Variables include age, sex, primary race (subjects of multi-racial background can only identify/select one primary race on eCRF, or choose “other” and specify), ethnicity, height (cm), weight (kg), body mass index (BMI), Baseline living situation category, and Baseline caregiver category.

The reported age will be calculated relative to the subject’s age at the informed consent date. Age and BMI will be presented as both continuous and categorical variables. Age categories will be presented as <70 and ≥ 70 years old. BMI categories will be presented as <25 , ≥ 25 to <30 , and ≥ 30 .

A listing of subject living situation and caregiver information will be provided.

8.2 Disease Characteristics at Baseline

Disease characteristics at Baseline will be summarized for the Safety Analysis Set and the Full Analysis Set using descriptive statistics. Variables include Baseline HAMD-17 total score, Baseline CGI-S, Baseline MMSE total score, Baseline SCOPA-NS score, Baseline SCOPA-DS score, Baseline SCOPA global sleep quality, and Baseline MDS-UPDRS Part III total score.

Baseline HAMD-17 total score, Baseline CGI-S, Baseline SCOPA global sleep quality, and Baseline MMSE total score will be presented as continuous and categorical variables. The categories will be displayed as follows:

- Baseline HAMD-17 total score: <24 and ≥ 24
- Baseline CGI-S: normal (1) to among the most extremely ill (7)
- Baseline SCOPA global sleep quality: very well (1) to very badly (7)
- Baseline MMSE total score: <25 and ≥ 25

PD and DPD disease history will include the following variables:

- Age (years) at onset of PD
- Duration (years) of PD
- Age (years) at onset of DPD
- Duration (years) of DPD

- Time (years) since first antidepressant treatment
- Current background antidepressant medication
- Duration (months) of current background antidepressant medication
- Ever had suicidal ideation or behavior (yes or no)
- Had suicidal ideation or behavior within past 6 months (yes or no)

Informed consent date will be used as the reference date for calculating the durations listed above.

The Massachusetts General Hospital (MGH) Antidepressant Treatment Response Questionnaire (ATRQ) is assessed at the Screening visit for subjects who are taking an SSRI/SNRI (i.e. adjunctive treatment). It is a clinician-assisted questionnaire used to determine response to antidepressant therapy. Drug type, generic name, drug taken during this current episode of depression (Yes/No), dose, and took at least this dose for at least 4 weeks (Yes/No), and the percentage of improvement in depression will be listed.

In addition, for all subjects lifetime antidepressant use and response will be collected, including start and stop dates, dose, units, and response ($\leq 25\%$, 26% to $< 50\%$, 50% to $< 75\%$, and 75% to 100%). These data will only be listed.

9 MEDICAL HISTORY

Medical and surgical history data will be coded using Medical Dictionary for Regulatory activities (MedDRA) version 19.0 or newer. The subject incidence will be summarized for each system organ class (SOC) and preferred term (PT) for the Safety Analysis Set and Full Analysis Set. A subject will be counted only once per SOC or per PT for the summary.

A listing of the SOC, PT, body system, verbatim term for the medical history condition/event, start and stop dates (when available), and an indicator for whether or not the condition is ongoing will be provided.

10 PRIOR, CONCOMITANT AND POST-TREATMENT MEDICATION

Summaries of prior, concomitant, and post-treatment medications will be provided for the Safety Analysis Set.

For a subject, a prior medication is defined as any medication with the start and stop dates prior to the date of the first dose of study drug. A Concomitant medication is defined as any medication with a start date prior to the date of the first dose of study drug and continuing after the first dose of study drug or with a start date between the dates of the first and last

doses of study drug, inclusive. Any medication with a start date after the date of the last dose of study drug will be considered as post-treatment medication. Prior, concomitant, and post-treatment medications will be summarized separately. Medications will be coded using the World Health Organization Drug Dictionary, version March 2017 or newer. The number and percentage of subjects taking each drug class (Anatomical Therapeutic Chemical Level 3) and medication PT will be tabulated. Multiple medication usage by a subject in the same category will be counted only once.

Background antidepressant therapies will be tabulated by medication PT and dose level.

